#### 7.3.2 Patient Identification Centres

There is potential for patients to be referred to the London and Birmingham treatment centres from both NHS and non-NHS institutions. These institutions will be listed as Patient Identification Centres. These institutions can then identify participants, can provide information about the study, can advertise the opportunity to participate in the study, (eg via posters in waiting rooms) or can put potential participants' in touch with the NEAT research team.

#### 7.4 Randomisation Procedure / Code Break

Randomisation will be requested by study sites online using a bespoke web based randomisation system hosted at the King's CTU.

Only study site staff authorised by the trial manager will be given login details to the randomisation system. Authorised staff will be allocated a username and password for the randomization system. Once a patient is consented, all baseline data collected and eligibility confirmed, the staff member will log into the randomization system (www.ctu.co.uk and click "randomisation – advanced" and select NEAT study) and enter the patient's details. The "help" section of the system has video demonstrations to aid new staff in using the system. Once randomized, the system automatically generates confirmation emails to key staff, with or without treatment allocation information, depending on their role in the study.

Emergency 24 hour code break will be via the eSMS emergency service (Medical Toxicology Information Service). Patients will be given a card to carry throughout the study, which gives details of the emergency code break telephone number to be called in the event of a clinical emergency necessitating code break. The eSMS 24 hour service number is [name]

## 7.5 Withdrawal of Participants

Participants have the right to withdraw from the study at any time for any reason. The investigator also has the right to withdraw patients from the study drug in the event of inter-current illness, AEs, SAEs, SUSARs, protocol violations, administrative reasons or other reasons. Upon withdrawal from the study the patient will be asked to complete the Treatment Outcomes Profile (TOP) and the withdrawal form.

[figure not shown]
It is understood by all concerned that an excessive rate of withdrawals can render the study uninterpretable; therefore, unnecessary withdrawal of patients should be avoided. Should a patient decide to withdraw from the study, all efforts will be made to report the reason for withdrawal as thoroughly as possible. Should a patient withdraw from study drug only, efforts will be made to continue to obtain follow-up data, with the permission of the patient.

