## 8.10 Structured clinical interviews and instruments

Participants will complete the following structured clinical assessments and instruments during the course of the study:

- DSM5 Axis I disorders: *major depressive episode* (current [2 weeks]; past; recurrent); *suicidality* (current [past month]; *panic disorder* (current [past month]; lifetime); *post-traumatic stress disorder* (current [past month]); *generalized anxiety disorder* (current past 6 months); *anti-social personality disorder* (lifetime), via SCID V. Screening and week 36.
- Drug and alcohol use 7 day form- Weeks 1 to 12.
- Minnesota Heroin [adapted] Craving Scale (MCCS for Heroin) Once at screening, then weekly until week 12, once at each follow up visit on weeks 16, 24 and 36 thereafter.
- Minnesota Cocaine [adapted] Craving Scale (MCCS) Once at screening, then weekly until week 12, once at each follow up visit on weeks 16, 24 and 36 thereafter.
- Borderline Personality Disorder Screener (BPD)30\* Screening.
- Short-form Buss-Perry Aggression Questionnaire (BPAQ-SF)31\* Screening.
- Barratt Impulsiveness Scale (BIS-11)32\* Screening.
- Addiction Dimensions for Assessment and Personalised Treatment (ADAPT) Screening, weeks 12 and 36.
- Montreal Cognitive Assessment (MoCA)33. Screening and week 12.
- HIV Risk-taking Behaviour Scale (HRBS) Screening, weeks 12 and 36.
- Scales (TOP) Screening, weeks 12, 36 and at withdrawal.
- Patient Health Questionnaire (PHQ-9) Screening, weeks 12 and 36.
- Generalized Anxiety Disorder Scale (GAD-7) Screening, weeks 12 and 36.
- Work & social adjustment scale (WSAS) Screening, weeks 12 and 36
- EQ5D  Screening, 12 and 36.
- Alcohol and Drug adapted Adult Service Use Schedule (AD-SUS). Screening, 12 and 36.
- Drug and alcohol use 28 day form Screening and weeks 16, 24, and 36 (and at withdrawal if withdrawal is after week 12)
- Heroin use form weeks 24 and 36 (and at withdrawal if withdrawal is after week 12)
- AE & conmed forms Ongoing.

The instruments above marked by an asterisk are for participant self-completion (assisted by a NEAT worker as required). These measures will be gathered and screened in the analysis as moderators of treatment response. The clinical team will use the information collected as part of the case formulation, treatment planning and tailoring process.

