## 11. Economic evaluation

Given that implanted XR-NTX is currently an unlicensed medication in Europe, and is more expensive than O-NTX, the relative cost-effectiveness of XR-NTX and O-NTX treatments will be assessed by including opportunity costs for stakeholders and comparing ratios of incremental opportunity costs (for all stakeholders) and incremental outcome (health related quality of life). Costs of the study interventions, external health services, and expenditure by the social and criminal justice sectors will be combined with the primary clinical outcome measure and quality adjusted life years to produce incremental ratios that will determine relative cost and cost-effectiveness.

Economic outcome assessments will be carried out after the 12-week treatment period and at the 36 week follow-up. The *a priori* primary economic outcome measure will be quality adjusted life years using the EQ-5D. The economic evaluation will take a broad policy perspective, including costs borne by hospital and community health and social services and the criminal justice sector, plus the costs of criminal activity. Detailed information on the resources associated with the treatments, including study medications, equipment, dispensing services, urine tests, nurse time, and contacts with key workers, medical, nurse and psychology staff, will be collected from clinical records. Resources external to the clinics, including staffed/supported accommodation, hospital contacts, community health and social services, criminal justice sector resources and crimes committed will be collected in interview with study participants at baseline, after the 12 week treatment period and at the week 36 follow up.

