#### 12.1 Power calculation

Estimated treatment effect size and retention to guide the required number of participants for NEAT was based on best available trial evidence and meta-analysis. The trial is designed to compare the effectiveness of extended-release naltrexone (XR-NTX) and oral tablet naltrexone (O-NTX) on an intention-to-treat basis at 12 weeks post-randomisation. There are two comparisons: XR-NTX vs. placebo, and XR-NTX vs. O-NTX. Based on a 2007 HTA systematic review and the naltrexone depot trial by [name] and her colleagues in the USA, the following assumptions were made:

- A. The mean percentage of heroin-free urine drug screens at 12 weeks post-randomisation will be approximately 0.30 (30%) in the placebo and O-NTX treatment arms, respectively, and 0.55 (55%) in the XR-NTX treatment 
- B. The standard deviations of the treatment groups will be of a similar magnitude We estimate the common standard deviation to be 30.
- C. The minimal clinically significant difference between the XR-NTX and O-NTX / placebo group will be a 25 point difference in percentage observable at 12 weeks post-randomisation, equating to an effect size of 0.8.
- D. An expected 40% attrition rate based on previous trial data.
- E. To control for multiple comparisons in the primary analyses, Bonferroni correction has been applied to the significance level reducing it by a factor 2. Thus the significance level will be considered at 2.5%.

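### The withdrawal assessment omits EQ-5D and AD-SUS, so a patient who formally leaves the study before week 12 has only a screening utility for the primary economic outcome

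*Protocol*

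**What the plan says.** Section 7.5 sets out what is collected when a patient leaves the study: "Upon withdrawal from the study the patient will be asked to complete the Treatment Outcomes Profile (TOP) and the withdrawal form". It treats stopping study drug only as a different case, in which follow-up is still attempted if the patient permits it.

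Section 8.10 gives the TOP a withdrawal time point ("Screening, weeks 12, 36 and at withdrawal"). It adds the 28-day substance-use form and the heroin-use form "and at withdrawal if withdrawal is after week 12". The EQ-5D has no withdrawal time point ("Screening, 12 and 36"), and neither does the service-use schedule: "Alcohol and Drug adapted Adult Service Use Schedule (AD-SUS). Screening, 12 and 36". The schedule in 6.3 agrees on both instruments.

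Section 11 states that the "primary economic outcome measure will be quality adjusted life years using the EQ-5D", and on timing: "Economic outcome assessments will be carried out after the 12-week treatment period and at the 36 week follow-up". It takes treatment resources from clinical records, and external service use and crime from interviews at baseline, week 12 and week 36. Section 11.2 anticipates last value carried forward for missing EQ-5D and single regression imputation for missing total cost, on the expectation of about 5% missing data, and allows other methods if that expectation fails. Section 12.1 assumes, for the sample size, "An expected 40% attrition rate based on previous trial data".

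**The concern.** Cost-effectiveness in QALYs serves primary objectives C and D (6.2.1). The withdrawal contact is the last planned opportunity to measure a patient who is leaving, and it collects neither of the instruments on which the utilities and the external costs depend.

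The screening utility is a doubtful substitute for what follows. It is taken when the patient must have a negative opioid urine test and must pass a naloxone challenge (7.1). A patient who then leaves a relapse-prevention trial may well have changed. If the screening value stands in for weeks 12 and 36, any deterioration is missed. If withdrawal also differs by arm, the error does not cancel in the incremental QALY. Differential withdrawal is plausible on the protocol's own account: section 5 describes poor retention on oral naltrexone, and 6.2.2 makes retention by arm a secondary objective.

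**Working it through.** **1. The three withdrawal lists side by side.**

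| Item at withdrawal | 7.5 | 6.3 schedule | 8.10 |
|---|---|---|---|
| TOP | yes | yes | yes |
| Withdrawal form | yes | yes | not listed |
| 7-day substance-use form | no | yes | no (weeks 1 to 12 only) |
| 28-day substance-use form | no | no | only after week 12 |
| Heroin-use form | no | no | only after week 12 |
| EQ-5D | no | no | no |
| AD-SUS | no | no | no |

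The lists differ on the substance-use forms. They agree in omitting the EQ-5D and AD-SUS.

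**2. What the 40% is for.** The plan states no figure for missing economic data caused by withdrawal. The 40% enters the power calculation for the urine outcome: 100 × (1 − 0.40) = 60 per arm. With SD 30 and two-sided 2.5%, the standard error is 30 × √(2/60) = 5.48. An effect size of 0.8 (24 points) gives 24/5.48 − 2.24 = 2.14, a power of 98.4%; 25 points gives 99.0%. The stated 98% is reproduced. The 40% is therefore total loss for the clinical outcome, and the protocol does not split it into formal withdrawal and silent loss.

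**3. How many patients.** The count is 300 × the share who formally withdraw before week 12. The share is not given, so these are assumptions: 10% gives 30 patients, 20% gives 60, 30% gives 90 and 40% gives 120. The last is the ceiling on the plan's own attrition figure. The 5% missing data expected in 11.2 would be 15 patients.

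**4. Weight of the missing values.** With trapezoidal QALYs over weeks 0, 12 and 36, and screening taken as week 0:
- screening: 6/52 = 0.115
- week 12: (6 + 12)/52 = 0.346
- week 36: 12/52 = 0.231
- total: 36/52 = 0.692

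Weeks 12 and 36 carry (0.346 + 0.231)/0.692 = 83% of the weight. For an early withdrawer, carry-forward fills both with the pre-randomisation value.

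**5. Illustrative size.** Assume that utility falls linearly by d between screening and withdrawal at week 6, then stays there to week 36. Carrying the screening value forward overstates that patient by d × (0.5 × 6 + 30)/52 = 0.635d.
- d = 0.05: 0.032 QALY
- d = 0.15: 0.095 QALY

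The arm mean is overstated by the withdrawal share times this amount:
- share 10%: 0.003 to 0.010
- share 20%: 0.006 to 0.019
- share 40% (ceiling): 0.013 to 0.038

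If formal withdrawal differed by 20 percentage points between two arms, the incremental QALY would be off by 0.20 × 0.635d = 0.006 to 0.019.

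**6. Dilution without differential withdrawal.** If withdrawal were unrelated to outcome, carry-forward of screening values would shrink the between-arm EQ-5D difference to (1 − m) of its size, where m is the share affected: 95% at m = 5%, 80% at 20%, and 60% at the 40% ceiling.

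**The case against.** Economic collection at baseline, week 12 and week 36 is stated consistently, and a short set of forms for someone who is leaving is a legitimate choice about burden. That is fair: this is a design choice that could be improved, not an error.

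Four stronger readings are tempting, and the protocol does not support them.

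- **That 40% of patients will have only a screening utility.** The 40% includes patients who simply stop attending. They have no withdrawal contact, so the fix recovers nothing for them. Patients who stop study drug only are still followed with permission, and 6.5.2 describes tracing aimed at those who have dropped out of treatment. Both groups may still give week 12 and week 36 values.
- **That an early withdrawer has no cost data.** Medication, dispensing, urine tests and staff contacts come from clinical records and remain up to the date of leaving. What is lost is external service use and crime.
- **That imputation would have nothing after randomisation to use.** Urine results, craving scores and weekly substance use up to withdrawal, plus the TOP, can serve as predictors. Section 12.4 foresees including variables associated with drop-out, and 11.2 allows other methods. These are indirect, however: no method can supply a post-randomisation utility that was never measured.
- **That the QALY figures estimate the bias.** The week-6 timing, the size of the drop, its persistence and the arm difference are all assumptions. A persistent drop also makes a withdrawal-date value exactly right by construction, which flatters the fix.

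The disagreement among the three lists is real, but it is a separate matter of documentation. The lists partly complement each other, and the EQ-5D gap would exist even if they matched.

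**Conclusion.** The point stands in a limited form, as a cheap improvement. A patient who formally withdraws before week 12 has one utility, taken before randomisation, for a primary outcome in which the later values carry 83% of the weight, and has no post-randomisation data on external service use or crime. The number of such patients is unknown and, on the plan's own attrition figure, cannot exceed 120 of 300. The illustrative error of 0.032 to 0.095 QALY per affected patient rests on an assumed drop of 0.05 to 0.15 by week 6 that persists.

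The fix would reduce the problem without removing it. For a week-6 withdrawal it would turn 6 of the 36 weeks (17%) into observed time; the other 30 weeks would still be imputed, but from a post-randomisation value. Clinical power is unaffected. Section 25 reports that the trial was wound down with six participants, so the practical value lies mainly in the design of the future implant trial that section 25.1 seeks to inform.

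**What to change.** Add the EQ-5D-5L to the withdrawal assessment, and AD-SUS where feasible, covering the period since it was last completed. If time is short, the EQ-5D-5L alone keeps most of the QALY benefit. Write one list of withdrawal forms and use it in 7.5, 6.3 and 8.10, stating which forms apply before and after week 12.

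In 11.2, place the withdrawal-date utility at its actual date in the QALY area under the curve, and use it as a predictor for later missing values in place of carrying the screening value forward.

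Both questionnaires are already used in the trial and the contact is already planned. The cost is a few extra minutes for a departing patient, who may decline.

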## 7.6 Expected Duration of Trial

Expected clinical participation for each participant is from consent until the final follow-up at 36 weeks (38 weeks in total). The study will begin when the first participant gives consent and will end when the last participant has finished the follow up assessment at 36 weeks.

#### 8. Trial Procedures

#### 8.1 Trial Flowchart

Treatment retention, adherence, heroin and cocaine craving scores, self-reported opioid, cocaine, amphetamine, benzodiazepine (and their active class metabolites via urine drug screening), and alcohol use, injection health risk behaviours, psychological health (depression and anxiety symptoms), and health-related quality of life results over the 12 weeks from randomisation and at 1, 3 and 6 months follow-up.

#### 8.2 Informed consent

Potential participants will be approached by a member of the clinical team. Each screening procedure will be overseen by the centre PI, or a medical officer reporting to the PI. Individuals failing screening will be allowed to enter screening once more (only) after 1 month.

A study doctor or trial nurse will implement the enrolment procedure and obtain informed consent. In cases when the taking of consent has been appropriately delegated to a non-physician, patients should be offered the opportunity to speak with the study doctor and the study doctor must document that they have confirmed the patient's eligibility in the medical notes, before the patient is randomised. The study information sheet will be read to the potential participant and discussed to ensure that he/she fully understands the purpose and key conditions of the trial, what is required and the risks and benefits arising from taking part. Each interested participant will receive an informed consent document with participant information and will be asked to read the information and ask questions.

If the patient wishes to participate, he/she will be required to sign the informed consent document prior to the conduct of any study-specific clinical procedures. This document will be witnessed and singed by the clinical worker.

In addition (and not a requirement of participation in the trial), participants will be asked if they are also willing to participate in collection of venous blood samples at intervals over the course of their treatment to enable study of blood levels of naltrexone and its metabolites. For participants wishing to participate, a written record of their consent will additionally be collected (as above). This will be considered separately.

## 8.3 Vital signs

In addition to the recording of demographic, social circumstances, referral information, substance problems treatment history and past 12-month DSM-V diagnostic criteria for opioid, cocaine, amphetamine, cannabis, sedative and alcohol dependence, and an instant result immunoassay test at screening, each participant will complete a physical exam administered by a clinic doctor or nurse, recording: height, weight, systolic/diastolic blood pressure and pulse rate (screening, 1, 2, 3, 4, 8, 12) and 12-lead ECG, measured after 5 minutes in a seated position (screening).

#### 8.4 Plasma monitoring

 $6-\beta$ -naltrexol is the primary metabolite of NTX. We plan to recruit, from the NEAT study sample, a sufficient number of participants to enable examination of plasma levels of  $6-\beta$ -naltrexol as well as of naltrexone itself, and to study the relationship to clinical benefit. Whilst outside the scope of the NIHR funded work, we present a summary of these analyses.

6- $\beta$ -naltrexol is the primary metabolite of NTX. Maintaining stable levels of this metabolite is the key aim of both O-NTX and XR-NTX and a key indicator of therapeutic response and benefit. Stable levels of 6- $\beta$ -naltrexol correlate with opioid craving levels and falling levels of 6- $\beta$ -naltrexol may correlate with attenuating patient engagement in the relapse-prevention therapeutic programme and drop-out. Subject to voluntary participant consent, assessment of 6- $\beta$ -naltrexol at regular intervals in the first month of treatment is important to document the intended action of active NTX and at later weeks to show: (1) the stability of the active implant; and (2) patient compliance with active O-NTX. Accordingly, 6- $\beta$ -naltrexol will be assessed on six occasions (weeks 1, 2, 3, 4, 8 and 12). At each clinical centre, EDTA blood (3-5 mL) will be collected via venepuncture. Samples will be centrifuged one portion to harvest plasma (1 mL) and the remainder is kept as whole blood (and store at -20 C in batches prior to laboratory processing at the co-ordinating centre [Toxicology Unit, King's College Hospital; [name]]).

# 8.5 Biological testing of opioid, cocaine, amphetamine and benzodiazepine use

At screening and thrice weekly until week 12 (plus all follow up weeks), participants will be asked to provide a clinic procedure supervised urine test for opioid, cocaine, amphetamine and benzodiazepine use. The study will use an instant result immunoassay device.

This is a tamper-proof device with a 48-hour detection window for opioids, cocaine, amphetamine and benzodiazepine metabolites with a temperature sensor required to register 33° - 38° C. This provides an instant qualitative test for recent drug use and will be used for the treatment responder/non-responder categorisation and outcome measure.

## 8.6 Naloxone challenge

Participants will be given naloxone prior to randomising the patient on week 1, with monitoring over 30 mins to check for no sign of opioid withdrawal. Individuals failing screening will be allowed to enter screening once more (only) after one month.

## 8.7 Breathalysed alcohol level

At screening and prior to the implant procedure, all participants will be breathalysed to exclude alcohol intoxication. Participants with a breathalysed alcohol level >0.35mg/l (35 Milligrams of alcohol per litre of breath) cannot proceed with screening or the implant procedure. NB: Individuals with breathalysed alcohol level >0.35 will be allowed to re-enter screening as clinically indicated

## 8.8 Self-reported substance use

Each participant will be asked to report their use of illicit opioids, cocaine, amphetamine alcohol and benzodiazepine.

At Screening and during weeks 1 to 12, data will be collected weekly for the 7 days prior to the visit, using the 7 day drug and alcohol use self-report form.

In the follow up stage, data will be collected at weeks 16, 24 and 36 for the 28 days prior to the visit, using the 28 day drug and alcohol use self-report form.

## 8.9 Molecular biomarker screening (genotyping)

Subject to voluntary participant consent, participants will be invited to allow the research team to undertake a genotyping targeting candidate pharmacodynamic biomarkers of addiction treatment response addiction risk vulnerability (including but not limited to OPRM1, OPRMD1; OPRK1; ORL1; CNR1 and DRD2 [stimulant risk], POMC [multiple substance risk]) and moderators of corticotropic stress and memory function (e.g. FKBP5, CRHR1 and NR3C1/2). DNA will be extracted from a single oral fluid sample collection and stored at the Social, Genetic and Developmental Psychiatric (SGDP) Centre at the Institute of Psychiatry, Psychology & Neuroscience on weeks -2 and 36. The sample collection procedure uses a pre-packed set of 10 cotton 'Q-Tip' buds. The participant opens the pack and rolls each Q-tip slowly and individually around each cheek area (5 on the left side and 5 on the right) and places each one in a 15cm plastic collection tube which holds all 10 Q-tips. The collection tube contains 10ml of neutral buffer solution. The cap is sealed by the participant and a bar code label is placed on the tube and sealed in a transit ziploc plastic bag for transport to the SGDP laboratory. Taking part in this aspect of the trial is entirely voluntary and an individual can enroll in the NEAT trial and decline to participate in the biomarker study. The biomarker study seeks to build on a research programme of studies in this area conducted at the trial coordinating centre (Institute of Psychiatry, Psychology & Neuroscience by Lead Investigator [name] [e.g. REC 10/H0808/73]) and with other university collaborators.

